### Expanded Safety Cohort (Cohort 3)

In the expanded safety cohort, approximately 400 participants will be randomized in parallel to 1 of 5 arms (in a 6:3:3:2:2 ratio to Arms 10, 11a, 11b, 12, and 13; [Table 7](#)). No pauses in enrollment for safety assessments are planned. Participants will receive either the selected 2×1 mL formulation based on the results from Cohorts 1 and 2, the selected 1 mL formulation for future clinical development, placebo, or the current Ad26/protein preF RSV vaccine (1×10^11 vp Ad26.RSV-A.preF/150 µg RSV-A preF protein).

Vaccine components evaluated in Cohorts 1 and 2 will be administered as 2 IM injections of 1 mL in the same deltoid muscle. However, once the optimal composition is selected, manufacturing formulation will be adjusted to ensure the administration of a single 1 mL vaccine dose in subsequent cohorts. Participants in Arms 11a and 11b will receive the selected vaccine in a 1 mL formulation and a second injection with placebo (1 mL) for blinding purposes. Cohort 3 thus will compare the 2×1 mL formulation of the selected combination of RSV vaccine components from Cohorts 1 and 2 (Arm 10) with the 1 mL formulation to be used for future clinical development (Arms 11a and 11b) with follow-up for 1 year post-vaccination in a double-blind placebo-controlled fashion. Participants in Arm 13 will receive the current Ad26/protein preF RSV vaccine (1×10^11 vp Ad26.RSV-A.preF/150 µg RSV-A preF protein) in a 1 mL formulation and a second injection with placebo (1 mL) for blinding purposes. Participants in Arms 11a, 11b and 12 will continue the study to assess durability and the effect of revaccination with follow-up up to 5 years post first vaccination. The timing of revaccination (at least 12 months relative to the first dose) will be based on Ad26/protein preF RSV vaccine clinical data.

For a subset of the participants, additional cellular immunogenicity assessments will be performed. This subset will be referred to as the Cellular Immuno Subset and will consist of approximately 240 participants: 40 participants per arm in Arms 10, 12 and 13, and 60 participants per arm in Arms 11a and 11b. The Cellular Immuno Subset will be recruited in study sites that have PBMC collection capability.

VAC18195 (JNJ 64400141/ JNJ 64213175/ JNJ-86051823/ JNJ 78991172)

Clinical Protocol VAC18195RSV1001 Original

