### Revaccination and Durability Cohort (Cohort 4)

In the revaccination and durability cohort, approximately 540 participants will be randomized in parallel to 1 of 3 arms (in a 5:5:2 ratio to Arms 14, 15 and 16; Table 8). No pauses in enrollment for safety assessments are planned. Participants in Arms 14 and 15 will receive the selected formulation for future clinical development on Day 1 and participants in Arm 16 will receive placebo on Day 1. Participants in Arm 14 (revaccination arm) and Arm 16 will receive the selected formulation at the same revaccination timepoint as participants in Arm 11a and 12 of Cohort 3. Participants in Arm 15 will receive placebo at the same revaccination timepoint as participants in Arm 11b of Cohort 3.

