### 9.2.4. Revaccination and Durability Cohort (Cohort 4)

The revaccination and durability cohort (Cohort 4) should provide sufficient data on the selected vaccine formulation to support future clinical development. To have approximately 150 participants available per arm for evaluating durability of immune response at end of the 5-year study period, and assuming a dropout rate of 10% per year, approximately 300 participants per arm are needed.

Corresponding arms of Cohort 3 and 4 will be combined (Arm 11a [Cohort 3] + Arm 14 [Cohort 4], and Arm 11b [Cohort 3] + Arm 15 [Cohort 4], respectively) for the evaluation of durability of the immune response. Having 75 participants in Arm 11a and 11b in Cohort 3 requires enrollment of 225 participants in Arms 14 and 15 in Cohort 4. Enrollment of 90 participants in Arm 16 (placebo) results in enrollment of in total 540 participants in Cohort 4. Placebo arms from Cohort 3 and 4, Arm 12 and Arm 16, respectively, will be combined in the analyses, as applicable.

Table 17 shows the probabilities of observing at least one AE for the selected formulation for future clinical development, at given true AE rates. This table shows that the current numbers give a reasonable probability to also observe less frequent events in the active arms in this cohort.

**Table 17: Probability of Observing at Least One Adverse Event for the Selected Formulation for Future Clinical Development, at a Given True Adverse Event Rate**

| True AE Rate (%) | Probability of Observing at Least One AE in N Participants (%) |        |        |        |        |
|------------------|----------------------------------------------------------------|--------|--------|--------|--------|
|                  | N=150                                                          | N=225  | N=300  | N=450  | N=600  |
| 0.5              | 52.9%                                                          | 67.6%  | 77.8%  | 89.5%  | 95.1%  |
| 1                | 77.9%                                                          | 89.6%  | 95.1%  | 98.9%  | 99.8%  |
| 2.5              | 97.8%                                                          | 99.7%  | 99.9%  | 100.0% | 100.0% |
| 10               | 100.0%                                                         | 100.0% | 100.0% | 100.0% | 100.0% |
| 25               | 100.0%                                                         | 100.0% | 100.0% | 100.0% | 100.0% |

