##### **9.4.3. Immunogenicity Analyses**

Immunogenicity data of corresponding arms from Cohort 1 and Cohort 2 will be combined in all analyses. Immunogenicity data of corresponding arms from Cohort 3 and Cohort 4 will be combined as applicable.

Continuous variables will be summarized descriptively. For continuous parameters, descriptive statistics of the actual values will be calculated at all timepoints, including geometric mean with 95% CI, median and quartiles, as applicable. Additionally, geometric mean fold rises from baseline and corresponding 95% CIs might be calculated.

For combined primary endpoint data of Cohort 1 and Cohort 2, geometric mean ratios between each active arm and Arm 1b will be calculated at all available timepoints, with corresponding 95% CI, as applicable. For Cohort 3, Arms 11a and 11b will be combined and the active arms will be compared to each other at all available timepoints up to 1 year after vaccination on Day 1, by means of geometric mean ratios with corresponding 95% CI. For durability and revaccination evaluation Arm 11a (Cohort 3) and Arm 14 (Cohort 4) will be combined, Arm 11b (Cohort 3) and Arm 15 (Cohort 4) will be combined, and Arm 12 (Cohort 3) and Arm 16 (Cohort 4) will be combined.

For immunogenicity analyses, baseline is considered as the last assessment pre-vaccination. Graphical representations of immunologic parameters will be made as applicable.

Geometric means per arm, and geometric mean ratios between active arms, with corresponding 95% CIs will be estimated via an analysis of variance (ANOVA) including all active arms, using log-transformed post-vaccination immune parameter response as dependent variable and study arm as independent variable. The means and differences in mean and CIs will be back-transformed (by exponentiation) to CIs around a GMT or geometric mean titer ratio (GMR). This analysis will be performed for all available assays and all time points, separately per assay. Data of the same arms from different cohorts will be combined, as applicable.

As a sensitivity analysis, the ANOVA may also be performed adjusting for the respective baseline titers, by including baseline titer as additional covariate.

For categorical variables, frequency tables will be presented.

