#### 5.3.3. Analysis Methods for the Primary Immunogenicity endpoint(s)

For Cohort 1, 2 and 4 the primary endpoint will be RSV neutralization antibody titers measured for RSV-A and RSV-B. In Cohort 3, RSV neutralization antibody titers are a secondary endpoint.

Data of corresponding arms from Cohort 1 and Cohort 2 will be combined in all analyses. Immunogenicity data of corresponding arms from Cohort 3 and Cohort 4 will be combined as applicable, too.

Descriptive statistics will be used for all arms to analyze the actual values (geometric mean, 95% CI, minimum, maximum, median and quartiles) and fold increase from baseline at all timepoints, as well as the percentage of participants with 2- and 4-fold increases from baseline. Additionally, the RSV-A/RSV-B antibody ratio will be reported by time points and the fold increase of RSV-A/RSV-B antibody ratio from baselines will be calculated at all timepoints.

For combined data from Cohort 1 and Cohort 2, geometric mean ratios for each active arm relatively to control Arm 1a and relatively to control Arm 1b, as well as relatively to each other will be calculated at all available timepoints along with corresponding 95% CI as applicable.

For Cohort 3, Arms 11a and 11b will be combined and the active arms (10, 11a+11b, 13) will be compared to each other at all available timepoints up to 1 year after vaccination on Day 1 by calculating the geometric mean ratios along with corresponding 95% CIs.

For durability and revaccination evaluation analyses, the following arms will be combined and compared to each other for all timepoints:

- Arm 11a (Cohort 3) combined with Arm 14 (Cohort 4);
- Arm 11b (Cohort 3) combined with Arm 15 (Cohort 4);
- Arm 12 (Cohort 3) combined with Arm 16 (Cohort 4).

Geometric means per arm of values for RSV-A, RSV-B and the ratio of RSV-A/RSV-B, geometric mean ratios for RSV-A, RSV-B and the ratio of RSV-A/RSV-B between all active arms along with corresponding 95% CIs will be estimated via an analysis of variance (ANOVA) using log-transformed post-vaccination immuno parameter response as dependent variable and study arm as independent variable. The means and differences in mean and CIs will be back transformed (by exponentiation) to CIs around a geometric mean or geometric mean ratio. This analysis will be performed by time points, separately per parameter. As a sensitivity analysis, the ANOVA may also be performed adjusting for baseline titer, age and sex.

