## **5.9. Planned Analyses**

The following analyses are planned:

- Primary analysis: 28 days post-vaccination safety and immunogenicity analysis up to D15 for humoral antibodies. This analysis will be performed when all participants in Cohort 1 and Cohort 2 have completed their 28-day post-vaccination visit. For primary analysis humoral immunogenicity will include baseline and Day 15 data, while safety analysis will be included the data up to Day 29 visit. Data from corresponding arms from the two cohorts will be combined. The goal of this analysis will be to select the vaccine formulation to be used in Cohort 3.

- Interim analyses:
  - 84 days post-vaccination immunogenicity analysis for Cohorts 1 and 2. Available immunogenicity data of all participants in Cohort 1 and Cohort 2 up to the Day 85 will be included in the analysis. 6-month post-vaccination safety and immunogenicity analysis for Cohorts 1 and 2. Available safety and immunogenicity data of all participants in Cohort 1 and Cohort 2 up to the Day 185 follow-up visit post-vaccination will be included in the analysis. This analysis may include immunogenicity data available from additional timepoints.
  - 1-year post-vaccination immunogenicity analysis for Cohorts 1 and 2. Immunogenicity data of all participants in Cohort 1 and Cohort 2 up to (and including) the 1-year follow-up visit post-vaccination will be included in the analysis.
  - 28 days post-vaccination safety and immunogenicity analysis for Cohort 3. This analysis will be performed when all participants in Cohort 3 have completed their 28-day post-vaccination visit.
  - 28 days post-vaccination safety and immunogenicity analysis for Cohort 4. This analysis will be performed when all participants in Cohort 4 have completed their 28-day post-vaccination visit.
  - 6-month post first vaccination safety and immunogenicity analysis for Cohorts 3 and 4. This interim analysis will include all safety and immunogenicity data from all participants in Cohorts 3 and 4, collected up to (and including) the 6-months follow-up visit post Day 1 vaccination.
  - 28 days post revaccination safety and immunogenicity analysis for Cohorts 3 and 4. This interim analysis will include all safety and immunogenicity data from all participants in Cohorts 3 and 4, collected up to (and including) the 28-day post-revaccination visit.

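### Before revaccination, SAP 5.3.3 gives two n=300 estimates of one identically treated regimen and no single pooled estimate of the formulation's response

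*SAP*

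**What the plan says.** SAP 5.3.3 pairs Arm 11a with 14, Arm 11b with 15 and Arm 12 with 16. For the durability and revaccination evaluation, "the following arms will be combined and compared to each other for all timepoints". Nothing limits this to timepoints after revaccination. Protocol 9.4.3 sets up the same pairs ("For durability and revaccination evaluation Arm 11a (Cohort 3) and Arm 14 (Cohort 4) will be combined", and likewise for the other two).

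The regimens are in Protocol 4.1 and its Tables 7 and 8. In Cohort 4, "Participants in Arms 14 and 15 will receive the selected formulation for future clinical development on Day 1". In Cohort 3, Arms 11a and 11b both receive the 1 mL formulation plus a 1 mL placebo injection on Day 1. The regimens part only at Day X, when 11a and 14 are revaccinated. In contrast, "Participants in Arm 15 will receive placebo at the same revaccination timepoint as participants in Arm 11b of Cohort 3". Day X is at least 12 months after the first dose.

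The SAP does pool across the future revaccination split in one place: 11a+11b, within Cohort 3, up to 1 year, for the formulation comparison. No immunogenicity text pools 14+15 or all four arms. For safety, Protocol Tables 17 and 18 do use N=450 and N=600 for this formulation.

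SAP 5.9 plans two analyses of these arms that fall wholly before Day X: a 28-day analysis of Cohort 4 and a "6-month post first vaccination safety and immunogenicity analysis for Cohorts 3 and 4".

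**The concern.** Up to the pre-dose Day X sample, 11a+14 and 11b+15 are two random halves of one treated population, so the true ratio between them is 1 by design. Comparing them at Days 15, 29, 85, 183 and pre-dose Day X says nothing about the vaccine.

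The question of interest in that period is how large and how lasting the response to one dose of the formulation is, relative to the placebo-first arms. The stated grouping answers it twice with half the sample and never once with the whole. RSV neutralization titres are the Cohort 4 primary endpoint, and early levels and decline are part of what they must show.

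Interpretation is also at stake. Protocol 6.3 allows group-level results to be shared from the 28-day interim analyses onward. A series of ratios between identically treated groups will sometimes give an interval that excludes 1, and such a result invites explanations it does not deserve.

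**Working it through.** **Inputs.** Enrolled N: 75 each in 11a and 11b, 225 each in 14 and 15, 50 in 12, 90 in 16 (Protocol Tables 7 and 8). SD of RSV-A2 VNA: 1.3 log2, a Day 29 figure used to size Cohorts 1 and 2 (Protocol 9.2.2). The documents give no SD for Cohorts 3 and 4, for RSV-B or for the placebo-first arms, so 1.3 is assumed for all of them. Intervals are 95% two-sided with z = 1.96.

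**1. The plan's own figures.** Protocol 9.2.4 states "Having 75 participants in Arm 11a and 11b in Cohort 3 requires enrollment of 225 participants in Arms 14 and 15 in Cohort 4": 75 + 225 = 300 per combined group. Its target of about 150 at year 5 gives 150 / (1 − 5×0.10) = 300 when the 10% yearly dropout is added up. (Compounding would give 150 / 0.9^5 = 254.) Table 14 also reproduces: 2^(±t(108) × 1.3 × √(2/55)) = 0.71 to 1.41. The nearby stated precision of about 0.36 log2 computes as 0.344 with z or 0.351 with t.

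**2. Are the two groups alike before Day X?** Within each cohort the paired arms have the same Day 1 regimen. Cohort 3 participants have an extra placebo injection that Table 8 does not list for Cohort 4, but they are 75 of 300 in both groups, so this is balanced. Days 15, 29, 85, 183 and the pre-dose Day X sample all come before the regimens part.

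**3. Precision of the GMT.** Half-width = 1.96 × 1.3 / √n, on the log2 scale.

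| Set | Split | Pooled |
|---|---|---|
| Cohorts 3+4 | n=300: 0.147 | n=600: 0.104 |
| Cohort 4 alone | n=225: 0.170 | n=450: 0.120 |

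As factors, 2^0.147 = 1.107 and 2^0.104 = 1.075. The interval is 1 − 1/√2 = 29% narrower whatever the SD. For SDs of 1.0 to 1.6 (assumed range) the split half-width runs from 0.113 to 0.181 and the pooled from 0.080 to 0.128. With 10% loss (n=270 and 540) the values are 0.155 and 0.110.

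**4. Precision of the ratio to 12+16** (n = 50 + 90 = 140). Half-width = 1.96 × 1.3 × √(1/n + 1/140).
- n=300: 0.261
- n=600: 0.239, about 8% narrower

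In Cohort 4 alone against Arm 16 (n=90), it falls from 0.318 (n=225) to 0.294 (n=450), about 7%. The placebo-first group limits this comparison.

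**5. The contrast between identical groups.** Half-width = 1.96 × 1.3 × √(2/300) = 0.208, so at an observed ratio of 1 the interval is about 0.87 to 1.15. There are five post-vaccination timepoints before revaccination. If independent, the chance that at least one interval excludes 1 is 1 − 0.95^5 = 23% for one subtype and 1 − 0.95^10 = 40% for two. Correlation between visits and subtypes lowers both.

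**The case against.** **Scope.** The SAP sentence opens by restricting itself to durability and revaccination evaluation, and following each randomised group from Day 1 to Year 5 is an ordinary way to display that. This is fair, but it does not supply a pooled estimate. If the early interim analyses lie outside that sentence, the remaining rule is an ANOVA by study arm, with 14 and 15 separate at 225 each. The wording that combines arms as applicable covers corresponding arms across cohorts, such as 11a with 14, and not 14 with 15.

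**Silence is not prohibition.** A reader might infer that the 28-day and 6-month analyses must report the formulation in halves. SAP 5.9 sets no grouping for them, and individual tables are left to a separate specifications document. A pooled table could still appear; the SAP just does not plan one.

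**No data are lost.** A reader might infer that half the participants are dropped or that the study falls short of its sample size. Neither is so. Both halves are reported, and the protocol's planned 300 per combined group is delivered. The 600 is an opportunity, not a target missed.

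**The split has a use.** The main ANOVA contains study arm only, and adjustment for baseline is an optional sensitivity analysis. A chance difference at the pre-dose Day X sample would carry into the unadjusted post-revaccination ratios, and readers should see it. This stands, so the contrast should be kept as a balance check and not deleted.

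**Conclusion.** The point holds as a free improvement of moderate size. Before revaccination the SAP's stated grouping splits one regimen into two and leaves out the estimate that best describes the formulation. Pooling makes the GMT interval 29% narrower. The ratio to 12+16, the only informative comparison among these groups in that period, gains about 8%. The absolute figures assume that the Day 29 SD of 1.3 log2 applies across arms, subtypes and visits, and they use enrolled N; the percentages do not depend on the SD if it is common to all arms.

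Two stronger readings are not supported. Pre-revaccination titres are not the whole Cohort 4 primary endpoint: SAP 5.3.1 names no timepoint, and the Protocol Section 3 objective covers groups with and without revaccination, so titres after Day X, where the split is needed, count as well. Nor is this a matter of bias or type I error: no hypothesis is tested, no margin or threshold depends on these intervals, and n=300 already gives a GMT interval of roughly ±11%.

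**What to change.** Amend SAP 5.3.3 as follows.

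- For post-vaccination timepoints up to and including the pre-dose Day X sample (and the possible extra 1-year sample if it falls before Day X), make 11a+11b+14+15 the main estimate and compare it with 12+16. In tables for Cohort 4 alone, use 14+15 against 16.
- Over the same timepoints, show 11a+14 beside 11b+15 only as a descriptive balance check, labelled as identically treated groups.
- From the first sample after Day X, keep the three-group comparison as written.
- State in SAP 5.9 that the 28-day Cohort 4 and 6-month Cohort 3/4 analyses use the pooled group.

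The cost is SAP wording and programming. No change to design, sample size, visits or data collection is needed.

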Blood will be collected from all participants to assess immune responses pre-vaccination and at the timepoints indicated in the [Schedule of Activities](#).

An internal DRC will be commissioned for this study to evaluate safety and reactogenicity data. If any of the pre-specified study vaccination pausing rules is met, further study vaccination will be paused and a DRC meeting will be convened (See Section 6.9). Refer to Committees Structure in [Appendix 3](#).

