#### **9.4. Statistical Analyses**

The statistical analysis plan will be finalized prior to sponsor unblinding of the locked database for the primary analysis and it will include a more technical and detailed description of the statistical analyses described in this section. This section is a summary of the planned statistical analyses of the most important endpoints including primary and key secondary endpoints.

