## 5. STATISTICAL ANALYSES

### 5.1. General Considerations

#### 5.1.1. Study phases

A baseline (or reference) value will be defined as the value of the last available assessment prior to vaccination on Day 1. If there was no immunogenicity assessment done pre-vaccination, the earliest assessment post-vaccination on Day 1 (but not exceeding Day 1) can be used as the baseline value for the immunogenicity analysis, if available.

The results of the safety analysis will be presented by phase. Immunogenicity results will be presented per scheduled time point as appropriate. Listings will be shown per phase and time point.

Study day or relative day is defined as follows:

- Study Day = visit date – date of Day 1 + 1; if visit date  $\geq$  date of Day 1 (date of vaccination).
- Study Day = visit date – date of Day 1; if visit date  $<$  date of Day 1 (date of vaccination).

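### Baseline titre is left out of the main GMT/GMR model and appears only in an optional, differently specified sensitivity run; adding it would be a near-free gain in precision

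*SAP*

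**What the plan says.** Protocol 9.4.3 has the geometric means and ratios "estimated via an analysis of variance (ANOVA) including all active arms, using log-transformed post-vaccination immune parameter response as dependent variable", with study arm as the only independent variable. SAP 5.3.3 keeps that model and applies it to "geometric mean ratios for RSV-A, RSV-B and the ratio of RSV-A/RSV-B between all active arms along with corresponding 95% CIs".

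Baseline adjustment is optional in both documents, but the covariates differ:

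- Protocol 9.4.3: "As a sensitivity analysis, the ANOVA may also be performed adjusting for the respective baseline titers".
- SAP 5.3.3: "As a sensitivity analysis, the ANOVA may also be performed adjusting for baseline titer, age and sex".

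SAP 6.2, which lists changes to the protocol-planned analyses, mentions only safety-laboratory grading.

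The baseline value is planned for everyone. Protocol 4.1 states: "Blood will be collected from all participants to assess immune responses pre-vaccination and at the timepoints indicated". SAP 5.1.1 defines baseline as the last value before vaccination on Day 1, with a fallback: "If there was no immunogenicity assessment done pre-vaccination, the earliest assessment post-vaccination on Day 1 (but not exceeding Day 1) can be used". The selection analysis already uses it; SAP 5.9 says: "For primary analysis humoral immunogenicity will include baseline and Day 15 data". SAP 5.3.3 also plans fold increases and 2- and 4-fold responder percentages. These use baseline, but they do not give a baseline-adjusted ratio between arms.

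**The concern.** The study tests no hypothesis and sets no margin. Protocol Section 3 wants a formulation that improves RSV-B responses without harming RSV-A responses, so the ratios and their intervals will be read directly. SAP 5.3.3 compares the active arms with Arm 1a, with Arm 1b and with each other. Protocol 9.2.2 justifies the sample size for this step by interval width alone.

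In that setting, an arm-only model gives up precision to the extent that a person's baseline titre predicts the post-vaccination titre. What is at stake is the width of the intervals used to choose the formulation, not the validity of the estimates.

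There is also a smaller point of pre-specification. The sponsor is unblinded at the primary analysis. As written, whether to adjust, and whether to follow the protocol's or the SAP's covariate list, remains open at that moment.

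**Working it through.** **Inputs.** 55 evaluable participants per arm and an SD of 1.3 on log2 (Protocol 9.2.2; the SD comes from Day 29 RSV-A2 results in an earlier study). There are ten active arms in Cohorts 1 and 2: 1a, 1b and 2 to 9. The correlation r between log baseline and log post-vaccination titre is not given; I assume 0 to 0.7. No SD is given for Day 15, RSV-B, the A/B ratio or later visits.

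**Reproducing Table 14 (two arms, arm-only).**
- SE of a difference = 1.3 × sqrt(2/55) = 0.248 log2.
- Half-width = t(0.975, 108) × SE = 0.4914 log2, a factor of 2^0.4914 = 1.406.
- Ratio 1 gives [0.71; 1.41], ratio 1.2 gives [0.85; 1.69] and ratio 1.5 gives [1.07; 2.11]. All six limits match, so the planned precision takes no credit for baseline.

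**Planned model (ten active arms, arm-only).** Half-width = t(0.975, 540) × SE = 0.4870 log2, a factor of 1.4015.

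**With log baseline as covariate.** The residual SD is multiplied by sqrt(1 − r²), one degree of freedom is lost, and average chance imbalance in baseline adds a small factor:
- Ten arms: t(0.975, 539) × SE × sqrt(1 − r²) × sqrt(1 + 1/538).
- Two arms: t(0.975, 107) × SE × sqrt(1 − r²) × sqrt(1 + 1/106).

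| r | Ten-arm CI factor around ratio 1 | Change in half-width, ten arms | Change in half-width, two arms |
|---|---|---|---|
| 0 | 1.402 | +0.1% | +0.5% |
| 0.2 | 1.392 | −1.9% | −1.6% |
| 0.3 | 1.380 | −4.5% | −4.2% |
| 0.5 | 1.340 | −13.3% | −13.0% |
| 0.7 | 1.273 | −28.5% | −28.2% |

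A simulation of the two-arm case (4,000 runs per r) gave +0.5%, −1.6%, −4.1%, −13.0% and −28.2%. A ten-arm simulation gave half-width ratios of 0.954, 0.867 and 0.715 at r = 0.3, 0.5 and 0.7, against sqrt(1 − r²) = 0.954, 0.866 and 0.714.

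**Break-even.** Adjustment stops costing anything at about r = 0.04 (ten arms) or 0.10 (two arms). A 10% narrowing needs r of about sqrt(1 − 0.9²) = 0.44.

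**In participants.** Ignoring the small imbalance term, 55 adjusted participants per arm match 55/(1 − r²) unadjusted: about 60 at r = 0.3, 73 at 0.5 and 108 at 0.7.

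**Effect on Table 14 (two arms, r = 0.7).** Ratio 1.2 moves to [0.94; 1.53] and still includes 1. Ratio 1.5 moves from [1.07; 2.11] to [1.17; 1.92] and excludes 1 either way.

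**The case against.** The strongest case against is that nothing here is wrong. The arm-only ratio is valid, it matches the precision calculation, and the plan is descriptive. Selection also weighs safety, manufacturability and ease of administration, and no rule depends on interval width, so no changed decision has been shown. Both documents already mention a baseline-adjusted run, and the SAP's added age and sex can be read as extra detail on an optional analysis. All of this stands, and it is why the point is an improvement and not a defect.

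The gain also rests on a correlation the documents do not give. At r of 0.2 or less it is under 2%. That stands too, but the worst modelled cost in the ten-arm model is 0.1%, so one need not know r to prefer adjustment.

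A third objection is that the gain assumes all 55 have a baseline. Missing immune data are not imputed (SAP 5.6), so people without one would leave the adjusted model. Since half-width scales with 1/sqrt(n), the 1.9% gain at r = 0.2 disappears if 1 − 0.981² = 3.8% lack a baseline, and the 4.5% gain at r = 0.3 disappears at 1 − 0.955² = 8.8%. No missing rate is given. Sampling is planned for everyone and there is a Day 1 fallback, so a large loss is speculative, but the rule must be written down.

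Finally, Protocol 9.4.3 calls baseline the last pre-vaccination assessment, which at revaccination visits could be read as Day X. The SAP's own definition is Day 1. That value precedes randomisation and so is a valid covariate at every visit.

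**Conclusion.** The point holds. The main model is arm-only, baseline adjustment is optional, and its covariates differ between protocol and SAP without being logged. Making log baseline titre a covariate in the main model is worth doing. The expected change in the 95% CI half-width runs from 0.1% wider (r = 0) to 28.5% narrower (r = 0.7), with about 13% at r = 0.5.

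That size rests on an assumed correlation, on 55 per arm all having a baseline, on one common slope across arms, and on a Day 29 RSV-A2 SD. The SAP's primary humoral analysis uses Day 15 and also covers RSV-B, where SD and correlation may differ. The gain is in precision only, and no Table 14 row changes whether it includes 1. I would class it as recommended rather than essential, with medium confidence because r is unknown.

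**What to change.** Amend SAP 5.3.3 before sponsor unblinding for the primary analysis, in line with Protocol 9.4: "The statistical analysis plan will be finalized prior to sponsor unblinding of the locked database for the primary analysis". The documents do not show whether that point has passed.

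- **Main model:** ANCOVA on log titre with study arm and the log Day 1 baseline (SAP 5.1.1) of the same parameter. For the RSV-A/RSV-B ratio, use the log baseline ratio. Say explicitly that Day 1 is the covariate at revaccination visits too.
- **Supportive model:** keep the arm-only ANOVA. It also shows whether the common-slope assumption matters.
- **Age and sex:** state whether that run is kept, so that only one covariate list applies.
- **Baseline below LLOQ:** state the value used as covariate, for example LLOQ/2, as SAP 5.6 does for geometric mean titres.
- **No baseline after the Day 1 fallback:** state the rule, for example left out of the ANCOVA and kept in the arm-only run.
- **Change log:** list the departure from Protocol 9.4.3 in SAP 6.2.

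The cost is SAP wording and one line in SAP 6.2, with no new samples or visits. Statistically it is one degree of freedom per model, plus any participants without a baseline. Adjusted geometric means per arm will differ slightly from the descriptive ones, so tables should be labelled accordingly.
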